5.2.5. Secondary Efficacy Analysis

All secondary endpoints will be summarized descriptively by treatment group and visit as defined for each period. Continuous endpoints will present baseline and actual value summaries and change from baseline (Period 1), Week 6 (Period 2), or Week 12 (Period 3) as appropriate. Proportions will be presented with denominators based on the number of subjects randomized to each treatment group.

The mean ALP values will additionally be represented graphically via a line chart for Period 2 and Period 3, with one page for each treatment group, with a line for each subject within the group charted individually, and with one line for the overall group. Period 2 will graph values for all scheduled visits from Baseline through Week 12 and Period 3 will graph values for all scheduled visits from Baseline through Week 18.

Absolute change in GGT from Baseline to Week 6 will be tested using a mixed model with repeated measures (MMRM) analogous to the primary endpoint ([Section 5.2.2](#)). This model will include fixed effects for treatment, IBD diagnosis, UDCA status, visit and treatment by visit interaction, with Baseline GGT value as a covariate. An unstructured covariance matrix will be used to model the repeated assessments over time. Denominator degrees of freedom will be adjusted using Kenward-Roger's method. Least Square (LS) Means and corresponding standard errors and 95% confidence intervals resulting from the model described will be presented at each visit. Differences in LS Means and corresponding two-sided 95% confidence intervals will be calculated at each visit comparing each active arm to placebo as well as comparing the HTD1801 1000 mg BID treatment group to the HTD1801 500 mg BID treatment group. The primary comparison of these treatment groups will be at Week 6.

Absolute change in GGT from Baseline to Week 6 will also be summarized by the subgroups as detailed in [Section 5.2.3](#).

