5.1.2 Baseline (immediately prior to dosing)

Potential subjects who have successfully completed all of the Screening procedures and have met all the eligibility criteria (see Sections 3.2.1 and 3.2.2) will be eligible for enrollment in the study. Prior to randomization, potential subjects will undergo the following Baseline procedures and assessments:

- An update of Medical History information
- Physical examination and vital signs
- An update of prior and concomitant medications
- ECG
- Confirmation of non-pregnant status for females

If the potential subject continues to satisfy the Inclusion/Exclusion criteria based upon these procedures and assessments stated above, those data will become part of the Baseline. Those potential subjects may be randomized and officially become subjects in the study. Subjects who have been taking UDCA will be instructed to discontinue UDCA prior to the Baseline visit. Subjects will again be instructed to avoid any use of the prohibited medications listed in Section 4.6 for the entire duration of the study, or until formally instructed otherwise.

Patients should also be cautioned about the use of glucose lowering drugs. The berberine component of HTD1801 is reported to lower blood glucose and may potentially cause hypoglycemia in patient taking other glucose lowering drugs at the same time. Patients who take glucose lowering drugs should be already aware of the most common symptoms of low blood sugar (dizziness, sweating, unusual hunger, shakiness, and a very rapid heartbeat) and should know how to react; in all these cases, however, patients should report these events to the Investigator.

Prior to dosing on Visit 2, the following additional Baseline procedures and assessments are to be conducted at the investigational site. All clinical laboratory samples are to be sent to the designated central laboratory for analysis. These Baseline central laboratory data will not be used to determine eligibility in the study as the newly enrolled subject has already been randomized. The additional pre-dose Baseline procedures are to include:

- CBC
- INR
- CMP that includes ALP, AST, ALT, bilirubin
- Standard serum lipid panel
- Partial Mayo Score
- Mayo Risk Score
- Plasma C-reactive protein(CRP) (only in patients with IBD)
- Stool sample for fecal calprotectin (FC) (only in patients with IBD). The stool sample testing may be completed separately from the site visit.

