1.2. SCHEDULE OF EVENTS

	Screening	Baseline	Initial Dosing Period			Dose-controlled Extension			Randomized Withdrawal			Follow-up
Visit Day	-28 to -1	0	Week 2	Week 4	Week 6	Week 8	Week 10	Week 12	Week 14	Week 16	Week 18	Week 22
Procedures												
Clinic visits	X	X			X			X			X	
Informed consent	X											
Eligibility criteria	X	X										
Demographics	X											
G6PD	X											
IgG4	X											
Urine drug test	X											
HIV/Hepatitis B, C	X											
Medical History	X	X										
Concomitant meds	X	X		X			X			X	X	
Physical examination	X	X		X			X			X		
Height/Weight/Vitals	X	X		X			X			X		
ECG	X	X		X			X			X		
Pregnancy testing	X	X								X		
Partial Mayo Score *	X	X		X			X			X		
CBC, CMP**, Lipids	X	X	X	X	X	X	X	X	X	X	X	
INR	X	X			X			X			X	

	Screening	Baseline	Initial Dosing Period			Dose-controlled Extension			Randomized Withdrawal			Follow-up
Visit Day	-28 to -1	0	Week 2	Week 4	Week 6	Week 8	Week 10	Week 12	Week 14	Week 16	Week 18	Week 22
Mayo Risk Score		X										
C-reactive protein *		X			X			X			X	
Fecal calprotectin *		X			X			X			X	
Randomization		X			X			X				
Dosing		X	X	X	X	X	X	X	X	X	X	
Adverse event monitoring		X	X	X	X	X	X	X	X	X	X	X
Telephone contact			X	X		X	X		X	X		X
Discharge											X	

* IBD subset only

** Including GGT

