5.2.4. Secondary Efficacy Endpoints

- Relative change in ALP from Baseline to Week 6
- Absolute change in ALP from Week 6 to Week 12
- Change in ALP from Week 12 to Week 18 for all subjects following the randomized withdrawal
- Proportion of subjects who achieve ALP of $< 1.5 \times \text{ULN}$ at the end of each period for each treatment group

- Proportion of subjects who achieve at least a 50% decrease in ALP at the end of each period for each treatment group
- Proportion of subjects who normalize ALP at the end of each period for each treatment group
- Absolute change in Gamma-Glutamyl Transferase (GGT) from Baseline to Week 6
- Relative change in GGT from Baseline to Week 6
- Absolute change in GGT from Week 6 to Week 12
- Change in GGT from Week 12 to Week 18 for all subjects following the randomized withdrawal
- Absolute change in serum total bilirubin at the end of each period for each treatment group
- In subjects with IBD, absolute change in fecal calprotectin (FC) from Baseline to Week 6
- In subjects with IBD, absolute change in FC from Week 6 to Week 12
- In subjects with IBD, absolute change in FC from Week 12 to Week 18 for all subjects following the randomized withdrawal
- In subjects with IBD who have elevated FC, the proportion of subjects who normalize FC at Weeks 6, 12, and 18 for each treatment group
- In subjects with IBD, absolute change in C-reactive Protein (CRP) from Baseline to Week 6
- In subjects with IBD, absolute change in CRP from Week 6 to Week 12
- In subjects with IBD, absolute change in CRP from Week 12 to Week 18 for all subjects following the randomized withdrawal
- In subjects with IBD who have elevated CRP, the proportion of subjects who normalize CRP at Weeks 6, 12, and 18 for each treatment group
- In subjects with IBD, absolute change in Mayo scores from Baseline to Week 6
- In subjects with IBD, absolute change in Mayo scores from Week 6 to Week 12
- In subjects with IBD, absolute change in Mayo scores from Week 12 to Week 18 for all subjects following the randomized withdrawal
- In subjects with IBD who have Baseline Partial Mayo score above 0, absolute change in Mayo scores from Baseline to Week 6
- In subjects with IBD who have Baseline Partial Mayo score above 0, absolute change in Mayo scores from Week 6 to Week 12
- In subjects with IBD who have Baseline Partial Mayo score above 0, absolute change in Mayo scores from Week 12 to Week 18 for all subjects following the randomized withdrawal

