7. CHANGES IN THE PLANNED ANALYSES

The following secondary endpoints listed in the protocol were removed, with replacements noted in parenthesis.

- Change in serum ALP between Baseline and Weeks 12 or 18, dependent upon the length of continuous treatment, compared to the placebo response during Period 1 (replaced with change from Week 6 to Week 12, and Week 12 to Week 18);

endpoint will be evaluated from descriptive summaries, but no statistical testing will be performed)

- Change in serum ALP between a new baseline at Week 6 and the final value at Weeks 12 for those subjects who received placebo during Period 1, compared to their initial 6-week placebo response (endpoint will be evaluated from descriptive summaries, but no statistical testing will be performed)
- Change in serum ALP between a new baseline at Week 6 and the final value at Weeks 12 for those subjects who received placebo during Period 1, compared to the similar change in the 500 mg and 1,000 mg treatment groups (endpoint will be evaluated from descriptive summaries, but no statistical testing will be performed)
- Change in serum ALP between a new baseline at Week 12 and the final value at Weeks 18 for all subjects following the randomized withdrawal (endpoint will be evaluated from descriptive summaries, but no statistical testing will be performed)
- Proportion of patients who achieve ALP of $<1.5 \times \text{ULN}$ (endpoint will be evaluated from descriptive summaries, but no statistical testing will be performed)
- Proportion of patients who achieve a 50% decrease in ALP (endpoint will be evaluated from descriptive summaries, but no statistical testing will be performed)
- The proportion of patients who normalize ALP (endpoint will be evaluated from descriptive summaries, but no statistical testing will be performed)
- Change in AST/ALT ratio (endpoint replaced with change in GGT)
- Change in serum bilirubin (endpoint will be evaluated from descriptive summaries, but no statistical testing will be performed)
- In subjects with IBD who have elevated fecal calprotectin (FC), change in FC compared to Baseline at Weeks 6 and 12, and the proportion of subjects who normalize FC at Weeks 6 and 12 (change in FC will be evaluated for all subjects with IBD, not just those with elevated FC; both endpoints will evaluated from descriptive summaries but no statistical testing will be performed)

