- For subjects who have elevated CRP at Baseline (for all subjects In the IBD subset): change from Baseline in CRP at Weeks 6 and 12, and normalization of CRP at Weeks 6 and 12 (change in CRP will be evaluated for all subjects with IBD, not just those with elevated CRP; both endpoints will evaluated from descriptive summaries but no statistical testing will be performed)
- For subjects with IBD who have Partial Mayo score above 0: Change from Baseline in Mayo scores at Weeks 6 and 12. (For Week 12, change from Week 6 will replace change from baseline; endpoint will evaluated from descriptive summaries but no statistical testing will be performed)

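### SAP 5.2.5 sets the number randomised as the denominator for every proportion, which contradicts the FC and CRP normalisation endpoints in 5.2.4 and the table rule in SAP 8

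*SAP*

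**What the plan says.** SAP 5.2.5 states, without exception: "Proportions will be presented with denominators based on the number of subjects randomized to each treatment group".

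SAP 5.2.4 lists two proportions with a narrower population: "In subjects with IBD who have elevated FC, the proportion of subjects who normalize FC at Weeks 6, 12, and 18" and "In subjects with IBD who have elevated CRP, the proportion of subjects who normalize CRP at Weeks 6, 12, and 18", each by treatment group.

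The markers exist only for part of each arm. The footnote to SAP 1.2 limits CRP and FC to the "IBD subset only", and Protocol 5.1.2 does the same, for example "Stool sample for fecal calprotectin (FC) (only in patients with IBD".

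SAP 7 broadens the continuous endpoints ("change in FC will be evaluated for all subjects with IBD, not just those with elevated FC"; "change in CRP will be evaluated for all subjects with IBD, not just those with elevated CRP"). It does not broaden normalisation, and it removes statistical testing for both.

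SAP 8 (Programming Conventions) has a second denominator rule. A frequency table shows its total count, percentages use that total, and missing observations are noted.

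On when a value counts as elevated, SAP 5.2.4 gives no time point for either marker. Protocol 3.3.1.2 (item 11) ties elevated CRP to Baseline. Item 10, on FC, attaches no time point to the elevation.

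**The concern.** A normalisation rate has meaning only among subjects whose marker was abnormal to begin with. The rule in 5.2.5 puts two other kinds of subject in the denominator: those without IBD, who have no FC or CRP sample, and those with IBD whose value was not elevated. Neither can ever be a responder.

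The displayed percentage then mixes the response rate with the proportion of the arm that happened to be eligible. Two arms with the same response rate can show different percentages only because they hold different numbers of eligible subjects. SAP 7 leaves these endpoints to descriptive summary, so the table is where a reader would look for the effect. IBD activity is a stated secondary objective (SAP 2).

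**Working it through.** The plan states no figure for these endpoints, so there is none to reproduce. The check has two parts.

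**1. The candidate denominators side by side**

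| Source | Denominator implied for FC or CRP normalisation |
|---|---|
| SAP 5.2.5 | all subjects randomised to the treatment group |
| SAP 4.1 | efficacy analyses use mITT: dosed, with at least one post-dose efficacy assessment |
| SAP 8 | the total count in the table module |
| SAP 5.2.4 | endpoint population: IBD subjects with an elevated value; no denominator written |

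If the module is restricted to the 5.2.4 population, the SAP 8 rule gives the subset denominator, or the part of it with a value at the visit. The 5.2.5 rule does not. The two sections therefore give different percentages for the same table, and neither names the subset.

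**2. The size of the dilution (illustration only)**

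Let N be the number randomised in the arm, m the number eligible (IBD and elevated), and r the number who normalise.

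- Shown rate under 5.2.5 = r/N = (r/m) × (m/N) = true rate × eligible share.
- The ceiling, when everyone eligible normalises, is m/N.

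Input from the documents: SAP 3.2 gives 42 + 17 = 59 randomised, and 59/3 = 19.7, taken as N = 20.

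Assumptions, not in the documents: 10 to 16 of the 20 have IBD, and 30% to 70% of those have an elevated value.

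- Eligible: 10 × 0.3 = 3, to 16 × 0.7 = 11.2 (about 11).
- Eligible share and ceiling: 3/20 = 15%, to 11.2/20 = 56%.
- A true rate of 50% shows as 0.5 × 15% = 7.5%, to 0.5 × 56% = 28%.

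Other assumptions give a similar picture. With an IBD share of 50% to 90% and an elevated share of 20% to 60%, the eligible share runs from 0.5 × 0.2 = 10% to 0.9 × 0.6 = 54%. A true 50% then shows as 5% to 27%.

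Unequal eligibility, with a true rate of 50% in both arms:

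- 5 eligible: 5 × 0.5/20 = 12.5% expected.
- 8 eligible: 8 × 0.5/20 = 20.0% expected.
- The expected gap of 7.5 points comes from eligibility alone. The subset denominator expects 50% in both arms.

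What the subset denominator cannot do: with 6 eligible per arm and a true 50% in both, the chance of equal responder counts is C(12,6)/4096 = 924/4096 = 0.226. The observed rates therefore differ by at least one responder (1/6 = 16.7 points) with probability 0.774.

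**The case against.** The strongest reply is that 5.2.4 already states a conditional proportion, and a specific definition would ordinarily override a general sentence. SAP 7 fits that reading, because it broadens the continuous changes and leaves normalisation alone. SAP 8 also leads to the subset if the module is restricted to it, and it already requires missing counts. Counts are shown next to percentages (SAP 5), so the numerator is visible under any denominator. Continuous FC, CRP and Mayo summaries also serve the IBD objective.

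Most of this stands, and it limits the weight of the point. A reader might infer that the tables will certainly carry diluted rates. The documents do not support that, because a programmer could reasonably use the subset. What does not fall away is that the only denominator sentence in the efficacy section says something else. It is a stated rule that does not fit the endpoint, and not merely a missing detail.

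A reader might also extend the point to the ALP responder proportions, since SAP 1.1 reports 3 subjects randomised but not dosed. That does not follow. SAP 4.1 analyses mITT subjects by the group to which they were randomised, so the phrase in 5.2.5 may simply mean assigned arm within mITT. At most this is a wording check.

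Finally, SAP 7 mentions Baseline for elevated CRP, but only in restating the protocol endpoint it replaces. The support for that time point is Protocol 3.3.1.2.

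**Conclusion.** The point holds as a contradiction over the denominator for two secondary endpoints. The rule in 5.2.5 does not fit the populations in 5.2.4 and conflicts with SAP 8. Followed literally, it multiplies the true normalisation rate by the eligible share of the arm.

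The size in this trial cannot be determined, because neither document gives the number with IBD or with an elevated value. The figures above show how the dilution works under stated assumptions; they do not estimate it.

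The impact is minor. The tables are secondary, descriptive and untested, and no test or primary result changes. A reader might infer that the correction would make the arms comparable on these endpoints; with subsets this small it would not. The correction gives the percentage its intended meaning and fixes the choice of denominator before results are seen.

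**What to change.** Add to SAP 5.2.5: *For FC and CRP normalisation, the denominator is the mITT subjects with IBD in the given treatment group whose value was elevated at Baseline.*

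Alongside it:

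- Confirm that Baseline is also the time point for FC. If elevation is to be judged at another time for Weeks 12 or 18, name that time.
- Reconcile 5.2.5 with SAP 8, so that one denominator rule applies to each proportion. SAP 8 already asks for missing counts. What needs saying is whether a subject with no value at the visit stays in the denominator, since SAP 3.3.4 allows no imputation of such values.
- For the ALP responder proportions, only check the word *randomized* in 5.2.5 against the mITT rule in 4.1.

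The cost is one sentence and a cross-check of two sections. No new data are needed and no test changes. The visible consequence is small FC and CRP denominators, about 3 to 11 per Period 1 arm under the first set of assumptions above.

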5.3. SAFETY

5.3.1. Adverse Events

AEs will be mapped to a Medical Dictionary for Regulatory Activities (MedDRA) version 20.1 preferred term (PT) and system organ classification (SOC). If a subject experiences multiple events that map to a single preferred term, the greatest severity grade according to the Common Terminology Criteria for Adverse Events (CTCAE) Version 4.0 will be assigned to the preferred term for the appropriate summaries. Should an event have a missing severity or relationship, it will be classified as having the highest severity and/or assumed related to study medication. The overall occurrence of any TEAEs, TEAE related to study drug, severe TEAEs, serious TEAEs, TEAE leading to discontinuation of study drug, and TEAE leading to death, alongside individual counts of each respective TEAE. The occurrence of TEAEs will be summarized by treatment group by SOC, and PT based on the treatment taken at AE start date. Summaries of the total number of subjects receiving each treatment and the average weeks of exposure for each treatment will be provided for context.

Separate summaries of each TEAE by period, TEAEs leading to the discontinuation of study, TEAEs related to study drug, and serious TEAEs will be generated and summarized by SOC and PT. The occurrence of TEAEs will be summarized by treatment group by SOC, PT, and Severity will also be summarized.

All adverse events reported will be listed for individual subjects showing verbatim term, PT and SOC. All AEs that occurred prior to the initiation of study treatment will be excluded from the tables but will be included in the listings.

Missing onset dates will be imputed as previously outlined in [Section 3.3.5](#) as required to determine treatment-emergent events.

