6.4 ASSESSMENT OF INTENSITY

The investigator will assess the intensity for each AE and SAE reported during the study on the basis of his or her clinical judgement. The classifications in Table 4 should be used in assigning intensity of each AE recorded in the case report form.

Formatt

Dele

Table 4. Classification of AEs by Intensity^a

Intensity	Definition		
Mild AE (Grade 1)	An event that is easily tolerated by the subject, causing minimal discomfort and not interfering with everyday activities		
Moderate AE (Grade 2)	An event that is sufficiently discomforting to the extent of interfering with normal everyday activities		
Severe AE (Grade 3)	An event that prevents the subject from performing normal everyday activities		
Life-threatening or disabling AE (Grade 4)	An event that, at the time of occurrence, put the subject at risk of death or resulted in a persistent or significantly disability or incapacity		
Death related to AE (Grade 5)	An event that resulted in death		

AE = adverse event

Any AE that changes in intensity or grade during a single occurrence of an AE will be recorded in the eCRF at the highest level experienced by the subject.

An AE that is assessed as severe should not be confused with an SAE. Severity is a category used for rating the intensity of an AE (such as mild, moderate, or severe myocardial infarction). However, AE itself may be of relatively minor medical significance, such as a severe headache. Both AEs and SAEs can be assessed as severe. An AE is considered serious when it meets one of the predefined outcomes described in Section 6.1.

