6.5 ASSESSMENT OF CAUSALITY

The investigator must estimate the relationship between the investigational product and the occurrence of each AE or SAE by using his or her best clinical judgment. Elements to consider for this estimate include the history of the underlying disease, concomitant therapy, other risk factors, and the temporal relationship of the AE or SAE to the investigational product. The investigator will also consult the Investigator's Brochure or product label for marketed products in estimating the relationship.

Because of reporting timelines, the investigator might have minimal information to include in the initial SAE report. However, the investigator must always make an assessment of causality for every SAE before the transmission of the SAE report. The investigator may change his or her opinion of the causality in light of follow-up information, with subsequent amendment of the SAE report. Causality assessment is

a From Common Terminology Criteria for Adverse Events, version 4.0

one of the criteria used to determine regulatory reporting requirements and should not be left blank on the eCRF. The same applies to AEs that are to be processed as SAEs.

Table 5 provides some definitions to use in the assessment.

Table 5. Assessment of Causality of AEs

Term	Definition
Possibly related	The AE may be related to the investigational agent(s) or intervention: the AE has a temporal relationship to the administration of the investigational agent(s) or research intervention.
Unrelated (or not related)	The AE is clearly not related to the investigational agent(s) or intervention: the AE has no temporal relationship to the administration of the investigational agent(s) or research intervention, and follows no known or suspected pattern of response, and an alternative cause is present.

 \overline{AE} = adverse event.

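### The SAP sets a missing AE severity to the highest category, which on the five-grade scale in use is death, without limiting the rule to fatal events

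*SAP*

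**What the plan says.** SAP 5.3.1 sets one rule for two missing items: "Should an event have a missing severity or relationship, it will be classified as having the highest severity and/or assumed related to study medication". The sentence before it names the scale and says how repeated events are combined: where several events in a subject map to one preferred term, "the greatest severity grade according to the Common Terminology Criteria for Adverse Events (CTCAE) Version 4.0 will be assigned to the preferred term". The imputed grade then has a table to appear in: "The occurrence of TEAEs will be summarized by treatment group by SOC, PT, and Severity will also be summarized". The same section plans summary rows for severe TEAEs and for TEAEs leading to death, but does not say which data field feeds the death row.

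Protocol 6.4 says the classifications in Table 4 "should be used in assigning intensity of each AE recorded in the case report form". The footnote to that table reads "From Common Terminology Criteria for Adverse Events, version 4.0", so the form and the SAP use the same scale. Table 4 runs from Grade 1 (mild) through Grade 3 (severe) and Grade 4 (life-threatening or disabling) to Grade 5, defined as "An event that resulted in death".

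SAP 3.3.4 says that, apart from its rules for dosing dates and for incomplete dates, nothing else will be imputed. It does not mention the severity and relationship rule in 5.3.1.

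**The concern.** Assigning the worst category to a missing severity is a familiar conservative convention, and it is harmless where the worst category is simply severe. Here the worst category is a statement about outcome. Giving Grade 5 to an event in a subject who survived is false, not cautious. The half of the rule that assumes relatedness does not have this problem.

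At stake is the accuracy of the severity tables in a trial with about 19 subjects per Period 1 arm, where a single Grade 5 entry would draw attention and have to be explained. The rule in 5.3.1 also disagrees with the general statement on imputation in 3.3.4, so the SAP needs an edit here in any case.

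**Working it through.** The plan gives no figure to reproduce. The check applies the rule to the scale and follows the result through the tables.

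**Step 1: the imputed value.** The ordered categories in Protocol Table 4 are {1, 2, 3, 4, 5}. Highest severity = max{1, 2, 3, 4, 5} = 5, the category for fatal events. Neither document defines highest differently, caps it, or makes it depend on outcome.

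**Step 2: the preferred-term rule.** Take a subject with one Grade 1 event and one ungraded event of the same preferred term. The ungraded event becomes Grade 5, and the greatest grade for the term is max{1, 5} = 5. The subject appears once for that term, at Grade 5. Several ungraded events of one term in one subject also give a single entry, so the number of false entries is at most the number of ungraded events.

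**Step 3: the weight of one subject in Period 1.**
- SAP 3.2: 42 + 17 = 59 subjects randomized.
- SAP 1.1: 3 randomized subjects had not started dosing. Assuming they are among the 59, 59 − 3 = 56 were dosed.
- With 1:1:1 allocation, 56 / 3 = 18.7 per arm, and 1 / 18.7 = 5.4%.
- If the 3 are not among the 59, 59 / 3 = 19.7 per arm, and 1 / 19.7 = 5.1%.

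**Step 4: the weight of one subject in the overall AE tables.** SAP sections 5 and 5.3.1 use the treatment being taken when the event started, so subjects contribute to more than one column. Assuming 56 dosed subjects, 1:1 allocation at each later randomization and no dropout:
- Each active dose: 56/3 from Period 1 plus half of the placebo arm, 18.7 + 9.3 = 28; 1 / 28 = 3.6%.
- Placebo: 56/3 from Period 1 plus half of those who started on active drug, 18.7 + 37.3/2 = 37.3; 1 / 37.3 = 2.7%.

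**Step 5: how often the rule would apply.** The documents give no count of missing grades. Protocol 6.4 asks the investigator to grade every AE, Protocol 8.1 has the monitor check that the forms are complete, and SAP 3.4 has the database cleaned before lock. Few grades should be missing.

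**The case against.** The strongest reply is that this is an undefined word, not an error. The SAP never writes Grade 5. It plans a row for severe TEAEs and a separate row for deaths, so the authors may have meant severe, and a sensible programmer would not give a living subject a grade defined by death. Other controls would also expose a false entry: every AE is listed by subject, results are independently programmed and checked by the lead statistician, and a death is a serious event reportable within 24 hours, so a Grade 5 entry without a matching report would stand out.

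Some of this stands. Severe may well have been intended, the rule should rarely be used, and a false entry would probably be noticed. But severe is the third of five categories in Table 4, so it is not what highest means on that scale. Independent programming verifies that the stated rule was carried out; it does not correct the rule, and two programmers could defensibly code 3 or 5. SAP section 8 asks for missing observations to be noted in frequency tables, but does not say that this overrides 5.3.1.

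A reader might go further and infer either of two things that the documents do not support:
- *That the count of TEAEs leading to death would be inflated, or would contradict the severity table.* The SAP does not say whether that row comes from grade or from outcome. If from outcome, the row is correct and the two tables differ; if from grade, they agree and both are wrong. Neither can be asserted.
- *That an imputed grade could trigger the trial stopping criteria in Protocol 7.4.* Those criteria use CTCAE grades, but nothing links them to values imputed for analysis.

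**Conclusion.** The rule is wrong as written. Followed literally, it records an ungraded non-fatal event as Grade 5 in the severity table and can raise the subject's whole preferred term to that grade. This conclusion rests only on the SAP sentence and Table 4.

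The practical effect is probably small, because few grades should be missing. Per affected subject it is about 5% of a Period 1 arm and about 3% to 4% or less of an overall treatment column, under the assumptions shown (about 56 dosed; no dropout for the overall columns). No efficacy result depends on it, and neither a false death count nor an effect on trial conduct is shown. It is a minor point, worth correcting because it is cheap to correct.

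**What to change.** Before database lock, amend SAP 5.3.1 to say:
- An event with missing severity is shown in the severity table either as Grade 3 (severe, imputed) with a flag, or in a separate missing category. Choose one. If the separate category is used, say how it ranks under the greatest-grade rule.
- Grade 4 is assigned to such an event only when the recorded seriousness criteria show that it was life-threatening or caused persistent or significant disability or incapacity. Both belong to Grade 4 in Table 4.
- Grade 5 is assigned only when the recorded outcome is fatal.
- The row for TEAEs leading to death is derived from AE outcome.

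Keep the assumption that an event with missing relationship is related. In SAP 3.3.4, name the severity and relationship rule as an exception to the statement that nothing else is imputed.

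The cost is a few sentences of SAP text and no new data. There is one small downside: under the Grade 3 option, some ungraded mild events may be counted as severe. The flag makes these visible.
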